to start time). The participant will attend an initial baseline visit, where informed consent will be completed and a baseline experimental visit of ad libitum smoking of one's preferred cigarette brand, and two additional visits later. The \geq 12-hour abstinence requirement was chosen because it controls for recent smoking exposure and produces optimal levels of smoking motivation that are sensitive to the experimental manipulations⁷ including the paradigm used in the current proposal, and prevents greater attrition and non-compliance relative to more prolonged periods.¹⁵⁷ Participants will be compensated \$45 for each in-person laboratory smoking visit in which they are eligible, or \$25 for Visit 1 if they are deemed ineligible. Participants will also be compensated \$35 for completing the baseline survey. Individuals will be compensated \$10 for each in-person visit (up to \$30).

Following are the standard procedures that have been adopted for the HPRC and OUM/OUHSC for all studies that will be facilitated in-person and would be utilized for this study in response to COVID-19.

PROCEDURE:

1. Employees will comply with all OUHSC COVID related policies and procedures as currently exist and as are revised in the future.
2. Efforts will be made to minimize face-to-face time with participants. When possible, consents will be sent to participants at their homes and reviewed by phone or zoom, as available. Additional items, including pregnancy tests, will also be shipped to the home, and reviewed over phone or zoom, when possible.
3. During scheduling, participants will be asked to wear a mask, if they have one available, to their appointments. For participants who do not have access to a face mask, they will be told that one will be provided. They will also be asked the questions from the OUM/OUHSC COVID19 Questionnaire (see attached in "Other Documents"). If the patient is symptomatic or has known direct contact with a person with COVID-19 they will be asked to consult with their PCP prior to re-scheduling their visit.
4. Participants will be instructed to call from their vehicle upon arrival for their appointment to prevent participants from congregating in the waiting room. They will also be verbally asked if any of their answers from the COVID-19 questionnaire have changed since their original completion. If the patient is symptomatic or has known direct contact with a person with COVID-19 they will be asked to reschedule their appointment.

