Participants will be asked and reminded not to send PHI via email or any other unapproved system. Research data will only be collected and recorded via approved data collection systems (e.g. REDCap and mHealth Insight)

Laboratory Visit /Session 1: Baseline Assessment and Ad Libitum Smoking. Visit 1 (between-subjects) will measure absolute reinforcing value (ARV) of menthol vs non-menthol cigarettes via a 60-minute ad libitum smoking session of one's usual cigarette type (menthol or non-menthol). Subjective response (e.g., smoking satisfaction, craving reduction, psychological reward, sensory effects like throat hit), smoking exposure (CO boost), and behavior (topography: number of puffs, total time smoked) will be measured.

After completing the initial screening over the phone, participants will be informed of the study procedures and invited to the lab to complete the three laboratory visits (If in-person data collection is occurring and if they choose to come to the laboratory). During scheduling for Visit 1/Session 1, they will be reminded to bring at least two of their cigarettes to the first study visit and will be asked to abstain from nicotine and tobacco products, and any other combustible product (e.g., cannabis) for at least 12 hours prior to each study visit. If they are going to attend an in-person session, they will be reminded to wear a mask and that they will be asked about any changes in the COVID-19 screener since they were first asked. If an individual selects virtual study sessions, they will be asked to complete the visit 1 procedures remotely using a remote topography device and iCO carbon monoxide reader to confirm smoking recency. In-person participants will provide a breath sample to measure carbon monoxide levels and asked when the last time they smoked a cigarette was. We will use password protected video conferencing to allow study staff to assist participants and complete this and the below procedures.

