After completing questionnaires, ARV will be measured by having participants smoke their usual brand of cigarette (*ad libitum*), which they will be instructed to bring with them to the first study visit. They will smoke through a mouthpiece of the Cress Smoking Topography Device, during a 60-minute smoking Visit or the SODIM Smoking Puff Analyzer Mobile SPA-M The CReSS or SODIM instrument will record puff volume, duration and velocity and inter-puff interval for each puff and their aggregate averages.⁷⁻¹⁰ Puff topography measures will be used to examine whether increased puff volume, duration, and lower inter-puff interval differ across menthol and non-menthol cigarettes. Before and after smoking, heart rate and blood pressure will be collected (if session is taken in person); exhaled carbon monoxide (CO boost), and subjective response to smoking (craving reduction, psychological reward, satisfaction, sensory effects) using the Cigarette Evaluation Questionnaire (CEQ). Exhaled carbon monoxide will be collected and measured in ppm immediately before and after smoking. At the completion of Visit 1, participants will be paid for the visit, and scheduled for study visits (V2 and V3).

Laboratory Visit or Session 2: Sampling Experimental Cigarettes and Cross-Price Elasticity Task. Participants will confirm abstinence by being asked the last time they smoked a cigarette in addition to providing a carbon monoxide measurement (CO \leq 8 ppm). Visit/Session 2 (within-subjects) will familiarize participants with the experimental cigarette (Camel Crush) by having them take a minimum of 3 and up to 5 puffs each of a menthol and non-menthol version (counterbalanced) and complete subjective ratings,

smoking exposure (CO boost), and behavior (topography: total time smoked). There will be a 20 minute washout period between each cigarette smoked, per our consultant's ([name]) paradigm protocol¹¹⁻¹⁴. Before and after smoking heart rate and blood pressure will be recorded (if session is taken in person), approximately 5 minutes after smoking subjective response, and CO boost will be recorded. After another 20 minute wait period from the last cigarette puff.

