In addition to the aforementioned recruitment methods, we will use BuildClinical, who will assist with recruitment by designing and managing targeted, GCP-compliant, IRB approved advertising. **BuildClinical** is a data-driven software platform that helps academic researchers recruit participants for research studies more efficiently using social media, software, and machine learning. BuildClinical utilizes study-specific advertisements to engage participants on digital platforms such as Facebook, Google, WebMD, etc., and redirect them to a study-specific landing page should they click it. On the landing page, the person can complete an online pre-screen questionnaire that gets routed into BuildClinical's platform. BuildClinical's Secure Socket Layer (SSL) software, which encrypts all inputted information, keeps participant information private and HIPAA compliant. BuildClinical's backend servers are stored in the USA at some of the most secure data centers in the world. The study team will access BuildClinical's platform to review and select qualified screening participants for additional screening. Interested individuals may then choose to enroll in the study by completing Informed Consent and HIPPA prior to scheduling a baseline lab or virtual session.

We have included the BuildClinical advertisement materials, pre-screening questionnaire, and study information landing page design and

IRB NUMBER: 10581
B NUMBER: 10581
IRB APPROVAL DATE: 02/14/2022
PROVAL DATE: 09/13/202112

content.[Inclusion/Exclusion criteria](#)

Inclusion criteria:

- (1) Ages 18 to 26;
- (2) Currently smoke cigarettes "somedays" or "everyday";
- (3) Started smoking "somedays" or "everyday" in the past 12-months or more than 12 months ago.
- (4) A strong preference for menthol or non-menthol cigarettes (i.e., smoke one type $\geq 80\%$ of the time).
- (5) Able to read and understand the informed consent
- (6) Willingness to abstain from nicotine containing products or other combustible products (e.g., smoked cannabis) for at least 12 hours prior to each in-person or virtual laboratory visit (confirmed by CO $\leq 8\text{ppm}$ for each in-person study visit in Phase 1). Will be rescheduled once if CO is not within acceptable range.

Exclusion criteria:

- (1) Current use of nicotine replacement therapy (NRT);
- (2) Currently pregnant or planning to become pregnant, or breast feeding (verified by pregnancy test at each study visit/session);

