Primary Outcomes: (a) number of days smoked cigarettes in the past 30-days, (b) number of cigarettes smoked in the past 30-days, (c) nicotine dependence; and (d) continuous ratings of harm perceptions (relative and absolute). **Secondary Outcomes:** (a) number and use of non-cigarette tobacco products used in the past 30-days (or onset of use of non-cigarette tobacco product use, if none at baseline), (b) number and use of non-cigarette flavored tobacco products in the past 30-days (including assessment of type of flavor used, like candy, fruit, alcohol, etc); and (c) intentions to use menthol cigarettes (among non-menthol smokers).

Intentions to use menthol cigarettes will also be assessed at follow-up among those reporting non-menthol as their preferred brand at baseline, using a modified 3-item algorithm: (1) “Do you think that you will try a menthol cigarette in the next 6-months? (2) “Do you think you will use a menthol cigarette anytime during the next month?” [we will assess next month and 6-months to increase variability]; (3) “If one of your best friends offered you a menthol cigarette, would you use it?” (“definitely yes,” to “definitely not”). Because of a range of possible responses, intentions may change among some

participants, making it a reasonable outcome measure. It is possible that some YAs may stop smoking over the course of the 6-months. We will examine baseline, laboratory, and EMA findings that set these individuals apart from those who continue to smoke, as such information could be useful to FDA.

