encrypted. Azure uses TDE (transparent data encryption) AES_256. The database on the app-related phone is encrypted with SQL-Cipher, which also underwent risk assessment and was approved for use by OUHSC. The OUHSC SSL certification for https encrypts data in transit. The only data that will be downloaded is data that can be accessed by the Battelle research team. Only research team personnel with specific roles can log in and download data. These steps will ensure the security of EMA data. Software will be downloaded onto each study phone so that phones can be remotely wiped if lost or stolen.

A Federal Certificate of Confidentiality is automatically provided by the NIH to protect against disclosures or release of data. All research personnel associated with this study have completed the Human Subject Protection Training Program or a training program approved by OUHSC. These are standard procedures used by PI of this application and they have been effective in the past.

Nicotine Withdrawal. Participants will be instructed to abstain from cigarette smoking for a minimum of 12 hours prior to each of the three visits in Phase 1. Some participants may experience nicotine withdrawal symptoms including irritability, difficulty concentrating, restlessness, anxiety, and depressed mood. Nicotine withdrawal symptoms can be uncomfortable, but they are not dangerous. Participants will be given information about the possibility of nicotine withdrawal symptoms at the end of the screening (before they attend the first baseline Visit) and again during the consent process.

Data Safety Monitoring Plan

Access to Identifiable Information and Data Storage:

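### Phase 1 requires 12 hours without any nicotine or tobacco, but the stated visit checks can detect only recent smoking

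*Combined protocol and SAP*

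**What the plan says.** The requirement is broad. Under Laboratory Visit/Session 1, participants being scheduled "will be asked to abstain from nicotine and tobacco products, and any other combustible product (e.g., cannabis) for at least 12 hours" before each study visit. Inclusion criterion 6 has nearly the same scope: "Willingness to abstain from nicotine containing products or other combustible products (e.g., smoked cannabis) for at least 12 hours", for in-person and virtual visits alike. It names CO of 8 ppm or below as the confirmation "for each in-person study visit in Phase 1). Will be rescheduled once if CO is not within acceptable range".

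The check is described most fully for Visit 2: "Participants will confirm abstinence by being asked the last time they smoked a cigarette in addition to providing a carbon monoxide measurement". The Nicotine Withdrawal paragraph, under Protection Against Risks, describes a narrower instruction: "Participants will be instructed to abstain from cigarette smoking for a minimum of 12 hours" before each of the three visits.

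The Phase 1 overview says the 12-hour rule was chosen "because it controls for recent smoking exposure and produces optimal levels of smoking motivation". The only nicotine product named in the exclusion criteria is current nicotine replacement therapy. Aim 3 lists as a secondary outcome "number and use of non-cigarette tobacco products used in the past 30-days", with onset of use counted for those who had none at baseline.

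**The concern.** Exhaled CO reflects combustion. The protocol itself uses the portable monitor as a marker of smoking recency. CO cannot show whether someone used an e-cigarette, smokeless tobacco or a pouch that morning, and a question about the last cigarette does not ask. Criterion 6 nevertheless treats CO as confirming abstinence from nicotine-containing products.

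The abstinence rule exists to bring participants to the Phase 1 sessions in a comparable state of smoking motivation. Recent nicotine from another source could plausibly alter craving reduction, satisfaction and reward after the test cigarette. Menthol preference is self-selected, so the two groups may differ in their use of other products. If they do, the Visit 1 contrast mixes a menthol effect with a difference in recent nicotine. Time since last nicotine is not among the candidate covariates listed for Aim 1, and the described procedures do not collect it.

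**Working it through.** The plan gives no figure to reproduce on this point, so the check is mainly a comparison of texts.

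**1. Requirement against check**

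| Place | Scope or check stated |
|---|---|
| Scheduling text, Visit/Session 1 | Nicotine, tobacco and other combustibles, 12 hours |
| Inclusion criterion 6 | Nicotine-containing and other combustible products, 12 hours; confirmed by CO |
| Nicotine Withdrawal paragraph | Cigarette smoking, 12 hours |
| Visit 1, in person | CO plus time of last cigarette |
| Visit 1, remote | Portable CO reading; no recency question stated |
| Visit 2 | Time of last cigarette plus CO |
| Visit 3 | CO plus when the participant last smoked |
| Table 2, abstinence row | CO only, all three visits |

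None of the checks covers non-combusted nicotine. No nicotine or cotinine assay is listed. Criterion 6 ties CO confirmation to in-person visits, but the remote procedures apply the same 8 ppm limit at the start of each remote session, so that difference is one of wording.

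**2. Who passes**

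Take a participant whose last cigarette was 13 hours ago and who vaped nicotine shortly before the session. The requirement is not met. The last-cigarette answer is truthful and satisfactory, and CO can be 8 ppm or below. The session goes ahead as abstinent. Such a person is eligible under the listed criteria, and the Aim 3 outcome definition allows for other tobacco use at baseline.

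**3. Which outcomes are exposed**

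- *Visit 1 ratings (absolute reinforcing value):* a between-subjects comparison of self-selected groups, so directly exposed. These ratings can also enter the Aim 3 models that use Phase 1 measures.
- *Visit 3 choice task:* each participant chooses between menthol and non-menthol puffs of the same brand. General satiation would act on both options, and the documents give no basis for a shift in relative preference.
- *Cross-price elasticity:* a hypothetical questionnaire given after 3 to 5 puffs of each of two cigarettes, so everyone has just had nicotine. Largely unaffected.
- *EMA mediators:* collected while participants smoke as usual, with no abstinence rule, and modelled separately in Aim 3. Unaffected.

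**4. Illustrative size for Visit 1**

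Input from the documents: 125 per group. Assumed inputs: the difference in the share of each group with undetected recent nicotine (0 to 0.20), and the shift such nicotine causes in a rating (0.3 to 0.8 SD).

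- Bias = difference in shares × shift. Smallest: 0 × 0.3 = 0. Largest: 0.20 × 0.8 = 0.16 SD.
- Standard error of the contrast, unadjusted and with no dropout: √(2/125) = 0.126 SD.
- Ratio at the upper end: 0.16 / 0.126 ≈ 1.3 standard errors.
- With equal shares the group bias is 0. If an assumed share of 0.10 to 0.30 in both groups is affected, the contrast shrinks by 10% to 30% if it vanishes entirely in those participants, and by 0% if it is unchanged in them.

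**The case against.** The failure needs a participant to go against an explicit instruction after being screened for willingness to follow it, and the documents do not show how often that would happen. This stands, and it is why the size is unknown. The lapse needs no dishonesty, though, because the question is never put, and under the narrower Nicotine Withdrawal wording vaping would not be a lapse at all.

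Four stronger readings are tempting, and the documents do not support them.

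- *That no visit data could reveal the problem.* Table 2 schedules the withdrawal scale (MNWS) and smoking-urge questionnaire (QSU) before smoking at all three visits, with heart rate and blood pressure in person, and the baseline survey covers current tobacco use. These may hint at recent nicotine. They are not used as abstinence checks and do not identify the product or time.
- *That all Aim 1 primary outcomes and all Aim 3 mediators are compromised.* The cross-price task and EMA measures are largely or wholly untouched, and an effect on the Visit 3 choice is not shown.
- *That the CO limit is also too weak to detect recent cigarettes in some-day smokers.* The documents give neither CO elimination rates nor typical readings. Except at remote Visit 1 as written, CO is paired with a recency question aimed at exactly that.
- *That the bias has a known direction.* Nothing in the documents says which group uses more of other products.

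It is also fair to say that the stated rationale begins with recent smoking exposure, which the existing checks do address, and that the Nicotine Withdrawal text is a risk paragraph, not the operating instruction.

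**Conclusion.** The point holds as a gap between requirement and verification: the stated confirmation rule cannot confirm the stated requirement. This rests on the text and on the fact that CO does not register non-combusted nicotine. The practical exposure is chiefly the between-group Visit 1 ratings of craving reduction, satisfaction and reward, and the Aim 3 models that use them.

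The documents establish neither size nor direction. The range of 0 to 0.16 SD rests entirely on the assumed shares and shift; its upper end slightly exceeds one standard error of the contrast and its lower end is nil. Balanced use leaves only attenuation or noise. Separately, the three descriptions of abstinence scope disagree and must be reconciled whatever the bias turns out to be. The point merits an amendment because the fix is cheap and visit-day recency cannot be reliably recovered afterwards. It does not invalidate Phase 1.

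**What to change.** 1. At every in-person and remote session, record the time of last use of each product type: cigarette, e-cigarette, smokeless or pouch, cigar or hookah, nicotine replacement, and smoked cannabis.
2. Apply the protocol's own 12-hour requirement and existing one-reschedule rule to that report as well as to CO.
3. Stop describing CO as confirming nicotine abstinence; describe it as a check on recent smoking. Align Table 2 and the text for all three visits, including remote Visit 1.
4. Reconcile the abstinence scope in the scheduling text, inclusion criterion 6 and the Nicotine Withdrawal paragraph.
5. Pre-specify how a session with reported use inside the window is handled in the analysis, and add a sensitivity analysis of the Visit 1 outcomes by time since last nicotine.

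The cost is one short question grid per session, a wording amendment, and a few more rescheduled visits among people who use more than one product. The limitation is reliance on self-report, so it will find only those who answer truthfully.

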Using a concurrent schedule, participants will be able to switch from working on one screen to the other as often as they desire. Consistent with relative reinforcement paradigms, the reinforcement schedule in the non-menthol earning screen will remain constant at a fixed ratio FR-25 (25 targets achieved to earn a point) while the reinforcement schedule for the menthol cigarette will increase (require more effort) with a progressive ratio schedule of PR-25 x over 10 trials, such that 25, 50, 75, 100, 125, 150, 175, 200, 225, and 250 targets have to be "hit" to earn a point.

The choice task determines how reinforcing menthol cigarettes are relative to non-menthol cigarettes (of the same brand) by the participant's willingness to work increasingly harder for puffs of a menthol cigarette vs nonmenthol cigarette. Reinforcement will be defined by the breakpoint, or the highest trial (out of 10 trials) that will be completed for menthol cigarette puffs.

The computer task will be performed until 10 trials are completed and a total of 10 points (or puffs) are accumulated. Per paradigm protocol, cigarette puffs earned are taken at the end of the procedure.²¹ Following the choice task, participants will be able to smoke the cigarette puffs they earned (up to 10 puffs). As in Visits 1 and 2, subjective response (e.g., smoking satisfaction, craving reduction, psychological reward, sensory effects like throat hit), smoking exposure (CO boost), and behavior (topography: number of puffs, total time smoked) will be measured.

To ensure that choice task responses are based on reinforcer preference rather than departure from the laboratory, the choice task will be followed by a 30-minute wait in the laboratory (if the session is taken in person). If the session is taken remotely, there may not be a 30-minute wait period. During this 30-minute wait period, participants will be queried about potential reactivity (i.e., behavior change or increased awareness of behavior and attitudes) to the laboratory visits with a brief survey. They will then be given instructions for the EMA phase of the study (Phase 2). During this training, participants will complete a practice survey from their phone. They will be given a wallet sized reference card containing the date range of the monitoring period, the lab study phone number, and a paper copy of the EMA questions and response options.

Table 2. Phase 1 Measures and Schedule of Events Under Normal Operating Procedures

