Phase 1 Measures	Laboratory Visit		
	1	2	3
Inclusion/Exclusion			
Informed Consent**	X		
Confirm Abstinence (exhaled CO ≤ 8ppm)	X	X	X
Urine Pregnancy Test	X	X	X
Monitoring for Adverse Events	X	X	X
Pre-Lab Smoking Measures			
Baseline Questionnaire Survey**	X		
Cigarette Purchase Task (part of the baseline questionnaire)**	X		
Behavioral Economic Choice Task			X
Minnesota Nicotine Withdrawal Scale (MNWS)	X	X	X
Questionnaire of Smoking Urges (QSU)	X	X	X
Vital Signs (heart rate (HR) and blood pressure (BP))***	X	X	X
Exhaled carbon monoxide (CO)	X	X	X

Smoking Measures			
Puff Topography	X	X	X
Post-Lab Smoking Measures			
Vital Signs (HR and BP)	X	X	X
Exhaled CO	X	X	X
Nicotine Delivery Effect Questionnaire (N=DEQ)	X	X	X
Duke Sensory Questionnaire	X	X	X
Cigarette Evaluation Questionnaire (CEQ)	X	X	X
MNWS	X	X	X
Other Measures			
Cross Price Elasticity Questionnaires		X	
30-minute wait period			X** (for inperson session)
Monitoring for Adverse Events	X	X	X

** Informed consent, baseline survey, and cigarette purchase task can be completed remotely (e.g., electronically) if participant enrolled during COVID-19 restriction on in-person data collection.

***vital signs will be assessed for in-person sessions.

Phase 2 Overview and Experimental Design

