Primary Outcomes: **(a)** the absolute reinforcing value (ARV) of menthol cigarettes from Visit 1, **(b)** the relative reinforcing value (RRV) of menthol cigarettes from Visit/Session 3 based on Choice Task responding; **(c)** RRV of own vs experimental brand based on price elasticity. ARV of menthol cigarettes will be operationalized as between subject differences in subjective ratings of menthol vs non-menthol cigarettes (satisfaction, reward, craving reduction, physical sensations) during the ad libitum smoking Visit. RRV will be measured by evaluating motivation to “work harder” for menthol versus non-menthol cigarette puffs or for one’s own brand from Visit 3. This is operationalized by the highest trial (breakpoint) that a participant successfully works for a menthol vs nonmenthol cigarette puff (or for their own vs experimental brand). Higher values reflect greater RRV of menthol cigarettes relative to non-menthol cigarettes (or their own brand vs the experimental brand. RRV of own vs experimental brand will be operationalized as cross-price elasticity of demand which measures the responsiveness of the quantity of experimental cigarettes that are self-reported to changing prices of the preferred cigarette brand.

Secondary Outcomes: **(a)** Total number of responses for the menthol versus the non-menthol-cigarette on the choice task **(b)** CO boost; and **(c)** puff topography (number of menthol versus non-menthol cigarette puffs consumed, number of minutes smoked, interval between puffs). Exploratory analyses will compare ARV and RRV.

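### Remote Visit 3 sessions may omit the post-task wait that protects the choice task, and no planned model accounts for session mode

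*Combined protocol and SAP*

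**What the plan says.** The section on Laboratory Visit 3 describes two screens between which participants may switch freely. Non-menthol points always cost 25 targets. Menthol points cost 25 targets at first and rise in steps of 25 to 250 at the tenth. The task ends once ten trials are completed and ten points earned, and the earned puffs are smoked afterwards.

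The same section gives the reason for the wait: "To ensure that choice task responses are based on reinforcer preference rather than departure from the laboratory, the choice task will be followed by" half an hour in the laboratory, for sessions held in person. It continues: "If the session is taken remotely, there may not be a 30-minute wait period". Table 2 agrees, marking the row "30-minute wait period" at Visit 3 for in-person sessions only.

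The outcome at stake is the relative reinforcing value of menthol, primary outcome (b) for Aim 1. The Phase 1/Aim 1 Analyses define it thus: "This is operationalized by the highest trial (breakpoint) that a participant successfully works for" a menthol versus a non-menthol puff. Laboratory measures of appeal and reinforcement also enter Step 3 of the Aim 3 regressions.

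Under the COVID-19 methods in Study Design, participants are asked at screening whether they want in-person or remote sessions. The candidate covariates for Aim 1 are cigarettes per day, nicotine dependence, race/ethnicity, gender and age of smoking onset. Aim 3 adjusts for the baseline level of the outcome and demographics. Phase order is to be controlled; session mode is not mentioned.

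**The concern.** The plan identifies a threat to one of its primary outcomes, adopts a safeguard, and then makes that safeguard optional for a self-selected subset, with nothing in its place. Because the wording is permissive, remote sessions may also differ among themselves, and nothing requires staff to record which ones included the wait.

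A participant at home is not waiting to leave a laboratory, but a video session also has an end that a participant may want to reach, after at least 12 hours of abstinence. If that wish affects responding, the breakpoint from a remote session partly measures something other than menthol's reinforcing value. The Aim 1 contrast by menthol preference could then shift with the mix of modes in each group, and the Aim 3 mediation models would use a laboratory predictor measured under two conditions but treated as one.

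**Working it through.** **Inputs from the plan.** Non-menthol cost: 25 targets per point. Menthol cost of the k-th point: 25k targets, which for k = 1 to 10 reproduces the plan's list from 25 to 250. Total points: 10. Planned size: 125 menthol and 125 non-menthol smokers. The plan gives no remote share, response rate, standard deviation, effect size or power for this outcome.

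**1. Work needed to finish at menthol breakpoint k.**
T(k) = 25 × k(k+1)/2 + 25 × (10 − k)

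- k = 0: 250; k = 1: 25 + 225 = 250
- k = 5: 375 + 125 = 500
- k = 8: 900 + 50 = 950
- k = 10: 1,375 + 0 = 1,375

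The all-menthol route costs 1,375/250 = 5.5 times the all-non-menthol route, or 1,125 more targets. From k = 1 upwards T(k) rises with every trial, and the quickest finish gives a breakpoint of 0 or 1. Hurrying can lower the menthol breakpoint but cannot raise it, and it does nothing to someone already at 0 or 1.

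**2. What the wait does to that incentive.** Assume 1 to 3 targets per second (not in the plan).

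- 1 per second: 250/60 = 4.2 min against 1,375/60 = 22.9 min. The saving is 1,125/60 = 18.8 min.
- 3 per second: 250/180 = 1.4 min against 1,375/180 = 7.6 min. The saving is 1,125/180 = 6.2 min.

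A fixed 30 minutes leaves these savings unchanged. It dilutes them: the slowest-to-fastest ratio falls from 5.5 to (22.9 + 30)/(4.2 + 30) = 1.55 at the slower rate and (7.6 + 30)/(1.4 + 30) = 1.20 at the faster.

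**3. Effect on the group contrast.** If remote sessions lower the breakpoint by s trials in both groups, the menthol-minus-non-menthol difference changes by −s × (remote share in menthol smokers − remote share in non-menthol smokers). Assumed s of 1 to 3 and share differences of 0.10 to 0.30 give 1 × 0.10 = 0.1 up to 3 × 0.30 = 0.9 trials in absolute value. The sign depends on which group goes remote more often. Equal shares give zero.

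**4. Illustration in terms of power.** Assume SD 2.5 trials, two-sided 5% and a true difference that gives 80% power at 125 per group: (1.960 + 0.842) × √(2/125) = 0.354 SD, or 0.89 trials. Take s = 1.

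- Remote 50% of menthol and 25% of non-menthol smokers: the difference falls by 0.25 and power is about 52%.
- Shares reversed: the difference is inflated by 0.25 and power is about 95%.
- Remote 25% in both groups, but non-menthol smokers already at the floor so that only menthol smokers shift: the difference falls by 0.25 and power is again about 52%.

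**5. Added noise.** A constant shift s in a fraction p of participants adds p(1 − p)s² to the variance. With p = 0.5 and the same SD, s = 1 adds 0.25 to 6.25 (4%) and s = 2 adds 1.00 (16%). Variation between people in how much they hurry would add more, and the plan gives no means of sizing it.

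**The case against.** The plan's stated worry is departure from the laboratory, which does not literally arise at home, and the text and Table 2 consistently confine the wait to in-person sessions. The waiver is a disclosed COVID-19 accommodation and not a contradiction. The asymmetric schedule is identical in both modes, so the 5.5 ratio does not measure the effect of the waiver. The wait removes none of the minutes saved by choosing non-menthol. Nor is it said to fall between the task and the earned puffs, so an abstinent smoker who wants those puffs gains by finishing quickly in either mode. A remote session does not stop with the task either: puffs, ratings and a carbon monoxide reading 10 minutes after smoking (Materials) still follow. Withdrawal and urge are measured before smoking, and dependence is a candidate covariate.

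All of this stands as a limit on the claim. A reader might infer that remote breakpoints are in fact pushed down, that home is where the pull to finish is strongest, or that the Aim 3 association would be attenuated or even reversed. The documents support none of these: they show a risk whose direction is known and whose occurrence and size are not. A reader might also infer that adjusting for mode could not help; in fact a mode term would remove an average shift, though not differences between people within remote sessions.

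What the objection does not answer is that the plan chose the wait to protect this outcome, does not argue that the threat vanishes remotely, and leaves a self-selected difference in procedure unrecorded and unadjusted. Phase order is a different variable from mode, since people who did EMA first may later attend in person.

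**Conclusion.** The point holds as a comparability problem of unknown size. Remote sessions may lack a safeguard that the plan considers necessary in person. If remote participants wish to finish early, their menthol breakpoints would be lower, because the quickest route (250 targets) yields a breakpoint of 0 or 1 and the all-menthol route needs 1,375.

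The mean contrast by menthol preference is biased only if remote shares or shifts differ between the groups. The 0.1 to 0.9 trial range and the power figures rest on assumed shifts, shares and SD, and illustrate sensitivity; they do not estimate what will happen. With equal shares and equal shifts, what remains is added noise in the Aim 1 breakpoint and in the laboratory predictor for Aim 3. This is an inexpensive improvement worth making, and not a flaw that invalidates the choice task.

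**What to change.** - Apply the same 30-minute wait to remote Visit 3 sessions, on the video call already in progress. Tell participants before the task that the wait follows whatever they choose. Do not tell them that session length is independent of their choices: a constant wait leaves total time dependent on the route taken, so this would be untrue unless total session time were fixed.
- Record session mode and whether the wait took place for every Visit 3.
- Include mode, and mode by menthol preference, in the breakpoint models, and mode in the Aim 3 models that use laboratory measures. Specify these terms in advance and exempt them from the rule that retains covariates only at p < .05.
- Run a sensitivity analysis that excludes remote breakpoints obtained without the wait. Report remote shares by preference group alongside it.

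The cost is protocol and analysis-plan wording, two data fields, and up to 30 more minutes per remote Visit 3. The reactivity survey fills only part of that time, and EMA training may already have been done by those who completed Phase 2 first. The sensitivity analysis will have a smaller sample and wider intervals.
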